9.4 Data Sources

The study will be conducted following a common protocol in populations covered by population-based health databases and cancer registries in four countries in Europe that are available for research and that provide access to health-related data (including prescription drug data). A summary of the characteristics and availability of data on study variables is presented in Annex 3. Data will be obtained from the following databases:

- The PHARMO Database Network in the Netherlands
- The Danish health databases
- The Swedish health databases
- The Clinical Practice Research Datalink (CPRD) in the UK

The PHARMO Institute in the Netherlands (<http://www.pharmo.com/>) has access to the PHARMO Database Network, a patient-centric data network that includes high-quality and complete information on (among others) patient demographics, drug dispensings, hospital morbidity, and pathology for more than 4 million residents of a well-defined population in the Netherlands for an average of 10 years. For a subset, clinical laboratory and GP information is also available. For the JOELLE Extension, data from the NCR, maintained by the Netherlands Comprehensive Cancer Organisation, are now available in the PHARMO Database Network and will be used to identify the stage of malignant melanoma, which will be used for a sensitivity analysis to assess surveillance bias (Section 9.7.2.5). Access to medical charts and other clinical data is available within the prerequisites of the Dutch privacy regulations.

In Denmark and Sweden, each national health care system provides universal coverage to all residents (5.7 million inhabitants in Denmark and 9.7 million inhabitants in Sweden in 2015). Health care coverage includes visits to GPs, specialists, hospital admissions, and hospital outpatient visits; drug costs are either partially or completely covered. A centralized civil registration system has been in place in each country for many years, allowing for personal identification of each person in the entire population and for the possibility of linkage to all national registers containing civil registration numbers, e.g., patient register, cancer register, prescription databases with drug dispensings, register of causes of death, and population registers [17]. Data collected in these registers can be made available for research purposes under the principles for protection and release of sensitive data [18,19].

The CPRD contains data recorded by general practitioners (GPs), who play a key role in the UK health care system as they are responsible for primary health care and referrals to specialists. The CPRD currently has research-quality records for 4.4 million active patients known to represent over 8% of the general population in the UK; it contains diagnostic and prescribing information recorded by the GPs as part of their routine clinical practice. Currently, over half of the CPRD has been linked to other UK health care data sets (e.g., National Cancer Registration Dataset, National Hospital Episodes Statistics, national mortality data), via the patient's National Health Service (NHS) number, sex, date of birth, and postal code [20]; CPRD Web site, <http://www.cprd.com/intro.asp>).

9.5 Study Size

We have updated the study size calculations for conducting the JOELLE Extension based on the incidence rates of each malignancy observed in Phase I and the updated annual number of users of tacrolimus in each data source. Calculations assume an extension of 4 years (through December 31, 2015), with a period of 3 years of inclusion of users and 1 year of follow-up. This ensures all users are followed for at least 6 months after applying a 6-month induction period. The total number of users in Phase I and the estimated number of users in the JOELLE Extension and the corresponding person-years of follow-up are presented in Table 3. In some databases, data beyond 2015 may be available and will be included in the study.

Table 3. Number of New Users of Tacrolimus and Person-years of Follow-up in Phase I (2002–2011) and Estimated Number in the JOELLE Extension (2002-2015)

	Phase I ^a		Extension ^b	
	Number of New Users	Person-years of Follow-up	Estimated Number of New Users	Estimated Person-years of Follow-up
Children aged < 18 years	19,948	50,316	24,412	133,285
Adults aged ≥ 18 years	66,127	198,400	98,788	551,369

^a Actual values.

^b Based on a 4-year extension (additional 3-year period of inclusion plus 1 year of follow-up) accounting for 6-month induction period.

In Table 4, we present the probability for each study endpoint to have an upper limit for the two-sided 95% CI of the rate ratio below the specific values of 2, 4, 8, and 16, according to the estimated number of users of tacrolimus, assuming a 4-year extension (additional 3-year period of inclusion plus 1 year of follow-up) and the incidence rates observed in Phase I.

For the pediatric population, the probabilities, although higher than in Phase I, are still low. The highest probability is for any lymphoma, with a 70% probability for having an upper limit of the 95% CI of the rate ratio below 8.

For the adult population, probabilities, already high in Phase I, have increased for the JOELLE Extension. The probability is 95% or higher for having an upper limit of the 95% CI of the rate ratio below 2 for NMSC, melanoma of skin, and non-Hodgkin lymphoma. For Hodgkin lymphoma and CTCL, the probabilities are 95% and 85%, respectively, for having an upper limit below 4.

Table 4. For Each Study Outcome, Probability That the Upper Limit of the 95% Confidence Interval of the Incidence Ratio is Below 2, 4, 8, or 16; JOELLE Extension (2002-2015)

Cancer Type by Age Group	Incidence per 100,000 Person-years ^a	Probability That Upper Limit of the 95% CI of the Rate Ratio is Below			
		2	4	8	16
Age < 18 years					
Skin, non-melanoma	0.5	0.05	0.09	0.15	0.23
Melanoma of skin	1.0	0.06	0.14	0.25	0.40
Lymphoma	2.1	0.09	0.24	0.46	0.70
Non-Hodgkin lymphoma	0.5	0.05	0.09	0.15	0.23
Hodgkin lymphoma	1.6	0.08	0.19	0.37	0.58
CTCL ^b	0.2	0.04	0.06	0.08	0.11
Age ≥ 18 years					
Skin, non-melanoma	286.2	1.00	1.00	1.00	1.00
Melanoma of skin	34.7	1.00	1.00	1.00	1.00
Lymphoma	25.6	0.99	1.00	1.00	1.00
Non-Hodgkin lymphoma	18.1	0.95	1.00	1.00	1.00
Hodgkin lymphoma	4.4	0.43	0.95	1.00	1.00
CTCL	3.1	0.33	0.85	0.99	1.00

CI = confidence interval; CTCL = cutaneous T cell lymphoma.

Note: Based on a 4-year extension (additional 3-year period of inclusion plus 1 year of follow-up) accounting for 6-month induction period.

^a Incidence rates based on results from Phase I.

^b Calculations could not be based on Phase I results because there were no cases of CTCL in children unexposed to topical tacrolimus. Incidence rates are from the age- and sex-specific incidences rates from the Surveillance, Epidemiology, and End Results (SEER) program of the National Cancer Institute in the United States (SEER*Stat version 7.05).

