This is a multinational cohort study of new users of topical tacrolimus, new users of topical pimecrolimus, users of topical corticosteroids with a diagnosis of atopic dermatitis or with at least two prescriptions of moderate- to high-potency corticosteroids within a period of 12 months, and nonusers of these medications. The study will be conducted with data from automated databases; cancer registries; and, for a subgroup, medical records. Stratification by exposure propensity scores will be used to control for confounding, including confounding by indication. An exposure propensity score estimates the probability that a given patient will receive a treatment conditional on measured covariates and can serve as a summary confounder variable. Because exposure propensity scores focus on the indication for use and nonuse of medications, they can be useful to control for confounding by indication. Propensity scores can perform better than conventional regression methods when the number of events relative to the number of potential confounders is small because rather than having to model the events with many variables, one can instead model the exposure, which may have ample data to accommodate a rich model [12]. This advantage may be important in this study, given the low number of events for each study endpoint expected in the

pediatric population. Data aggregated by strata of propensity scores estimated in each database will be used to estimate overall effects across the four data sources.

It is convenient when trying to take into account induction periods to follow an inception cohort, in which only initiators of the medication of interest are followed. A new-user design also prevents potential survival bias secondary to the inclusion of prevalent users who are “survivors” of earlier periods of treatment. In addition, a new-user design allows a more accurate estimation of propensity scores and control of confounding by indication, as covariates are measured at the initiation of therapy and are not affected by the exposure itself.

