9.7.2.3 Estimation of Incidence Rate Ratios

The coordinating center will use Mantel-Haenszel methods for the pooled analysis. Incidence rate ratios and 95% CIs will be estimated, stratifying by deciles of propensity scores, age categories, sex, and database research partner. To control for confounding, the Mantel-Haenszel analysis will provide pooled estimators that summarize the effect of exposure across strata of propensity scores and database partner. Incidence rate ratios will be estimated separately for children and adults. Crude and adjusted incidence rate ratios and 95% CIs for each study endpoint will be estimated, comparing the incidence rates for each exposure category (ever use, single use, and switcher/multiple use) of topical tacrolimus and topical pimecrolimus with the rates in the corresponding corticosteroids cohort. The analysis will focus on the estimation of incidence rate ratios comparing the incidence rates for each category of cumulative dose and duration of exposure to tacrolimus and pimecrolimus (e.g., low, medium, high) with the rates in the corresponding corticosteroids cohort. These rate ratios will be estimated separately for the periods of ever use, single use, switching/multiple use, and combined multiple use.

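### Pediatric rows of Table 4 rest on Phase I person-years and a large-sample formula that is invalid at about 0.1 to 3 expected exposed cases; against the extension's true probabilities they err in both directions

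*Protocol*

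**What the plan says.** Section 9.5 tabulates "the probability for each study endpoint to have an upper limit for the two-sided 95% CI of the rate ratio below the specific values" 2, 4, 8 and 16. The title of Table 4 assigns it to the JOELLE Extension (2002-2015), and its note reads "Based on a 4-year extension (additional 3-year period of inclusion plus 1 year of follow-up) accounting for 6-month induction period". The section says that the calculation uses the estimated number of tacrolimus users and the incidence rates seen in Phase I. It names no formula, no true rate ratio and no comparator ratio.

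Table 3 gives users and person-years for Phase I and then for the extension: "Children aged < 18 years 19,948 50,316 24,412 133,285" and "Adults aged ≥ 18 years 66,127 198,400 98,788 551,369".

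The text of 9.5 describes the pediatric probabilities as higher than in Phase I but still low. It puts the best one, any lymphoma below 8, at 70%. Section 9.9 repeats that pediatric precision improves but remains low. The opening of Section 9 justifies propensity scores partly by sparse pediatric data, "given the low number of events for each study endpoint expected in the" pediatric population. Section 9.7.2.3 adds: "Incidence rate ratios will be estimated separately for children and adults".

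**The concern.** The pediatric rows carry rates of 0.2 to 2.1 per 100,000 person-years, so even the extension expects fewer than three exposed cases for any endpoint. A normal approximation with a fixed standard error cannot describe a confidence limit at such counts, because often one arm has no case and a log-scale Wald limit does not exist. The protocol shows how sparse the data are: footnote b of Table 4 reports no CTCL case among unexposed children in Phase I.

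Children were the focus of the follow-up measure behind this study (Section 7.1), and Section 9.9 makes the upper confidence limit a main parameter for interpretation. Table 4 is the only quantitative statement of what the extension could rule out in children.

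**Working it through.** **Inputs.** Person-years from Table 3: children 50,316 (Phase I) and 133,285 (extension); adults 198,400 and 551,369. Rates and printed probabilities from Table 4. Matching ratio up to 4:1 from Section 9.2.3.2. Assumed, because 9.5 does not state them: true rate ratio 1, independent Poisson counts, comparator ratio *r* varied.

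**Reproducing Table 4.** With A = rate × exposed person-years and B = *r*A, P = Φ(ln(limit)/√(1/A + 1/B) − 1.96).

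Any lymphoma below 8, Phase I person-years, *r* = 3:
- A = 2.1 × 50,316/100,000 = 1.057 and B = 3.170.
- SE = √(0.946 + 0.315) = 1.123.
- P = Φ(2.079/1.123 − 1.96) = Φ(−0.109) = 0.457; printed 0.46.

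Over all 48 cells the largest gap is 0.011 at 3:1 and 0.007 at 3.2:1 (pediatric cells alone, under 0.007 at either). With extension person-years the largest gap is 0.25 to 0.43 for ratios from 1:1 to 4:1. The same lymphoma cell becomes A = 2.799, SE = 0.690, P = Φ(1.05) = 0.854.

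**Expected exposed pediatric cases (Phase I, then extension person-years).** CTCL 0.10, 0.27; NMSC and NHL 0.25, 0.67; melanoma 0.50, 1.33; HL 0.81, 2.13; any lymphoma 1.06, 2.80. At 3:1 the chance that at least one arm has no case is 0.37 (lymphoma) to 0.97 (CTCL) at Phase I person-years. At extension person-years it is still 0.58 for NMSC and NHL and 0.87 for CTCL.

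**Floor.** As A and B go to 0 the formula tends to Φ(−1.96) = 0.025 at every limit. Much of the 0.04 to 0.05 printed below 2 for CTCL, NMSC and NHL is this floor.

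**Real intervals.** For each pair of counts (a, b), the exact conditional upper limit is *r*·p/(1 − p), with p the 0.975 quantile of Beta(a + 1, b). The mid-P limit is defined analogously. The probabilities of all pairs with the limit below the threshold are summed.

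A hand check for NMSC below 2, extension, 3:1: with a = 0 the limit is 3(0.025^(−1/b) − 1), which is below 2 only if b ≥ 8. The comparator mean is 2.0, so P(b ≥ 8) ≈ 0.0011, and P(a = 0) = 0.514. The product is about 0.0006, which is nearly all of the total.

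Results at 133,285 person-years (3:1, then 4:1):

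| Cell | Printed | Formula | Exact | Mid-P |
|---|---|---|---|---|
| NMSC, NHL below 2 | 0.05 | 0.071, 0.073 | 0.001, 0.000 | 0.009, 0.003 |
| NMSC, NHL below 4 | 0.09 | 0.164, 0.172 | 0.029, 0.030 | 0.080, 0.075 |
| CTCL below 2 | 0.04 | 0.049, 0.051 | 0.000, 0.000 | 0.000, 0.000 |
| CTCL below 4 | 0.06 | 0.090, 0.093 | 0.001, 0.001 | 0.007, 0.004 |
| CTCL below 8 | 0.08 | 0.151, 0.159 | 0.038, 0.019 | 0.038, 0.076 |
| Lymphoma below 8 | 0.46 | 0.854, 0.875 | 0.845, 0.911 | 0.888, 0.935 |
| HL below 8 | 0.37 | 0.749, 0.775 | 0.733, 0.813 | 0.780, 0.848 |
| Melanoma below 16 | 0.40 | 0.792, 0.817 | 0.716, 0.784 | 0.770, 0.864 |

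At 3.2:1, mid-P for CTCL below 4 is 0.009.

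**Two separate comparisons.**
- *Formula against real interval at the same person-years.* At Phase I person-years (3:1 and 3.2:1) the formula is too high in 24 of 24 cells (exact) and in 23 to 24 (mid-P). At extension person-years (3:1 to 4:1) it is too high in 20 to 24 (exact) and in 12 to 20 (mid-P).
- *Printed values against the extension's real probabilities.* At 4:1 the printed value is too low in 14 of 24 cells (exact) or 16 of 24 (mid-P), and too high in the rest.

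**The case against.** **A reader might infer that Table 4 mostly overstates pediatric precision.** That describes the formula's error at Phase I person-years. It does not describe the printed table set against the extension it claims to cover. There the short person-years pull the other way, and more cells are too low than too high.

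**Nor is every printed figure far from a real interval.** At Phase I person-years and 3.2:1, mid-P gives 0.45 and 0.70 for lymphoma below 8 and below 16, against 0.46 and 0.70 printed. Some apparent contrasts also depend on the inferred ratio: NMSC below 16, printed 0.23, is 0.05 exact at 3.2:1 but 0.14 at 3:1, because the counts are discrete.

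**The person-years are the larger fault for the commoner endpoints.** This stands. For lymphoma below 8 at 4:1, correcting them moves 0.46 to 0.875, and an exact interval then adds about 0.04. But it does not make the formula acceptable at low thresholds or for CTCL.

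**The inputs are inferred.** True, but extension person-years would need a comparator ratio of about 0.4:1 to give the printed values, which does not fit matching up to 4:1.

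**The practical consequence is limited.** The protocol already calls pediatric precision low, and 4 to 5% already reads as unlikely. Exact and mid-P also differ from each other, and the planned analysis is Mantel-Haenszel. These points limit the severity; they do not make the printed figures right.

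**Conclusion.** The concern holds as a fault in the stated precision, not as a one-sided exaggeration. Two errors combine in the pediatric rows: Phase I person-years in a table labelled for the extension, and a normal approximation used where it is not valid.

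The following hold at 3:1, 3.2:1 and 4:1 under both exact and mid-P limits:
- The chance of excluding a doubling is at most 0.001 (exact) or 0.009 (mid-P) for NMSC and NHL, against 0.05 printed, and 0.000 for CTCL, against 0.04.
- CTCL below 4 is 0.001 to 0.009, against 0.06.
- Lymphoma, HL and melanoma below 8 and below 16 are printed too low, chiefly because of the person-years.
- Correcting the person-years alone would still misstate the low-threshold and CTCL cells. At 4:1 the formula gives 0.17 for NMSC and NHL below 4, against 0.03 exact or about 0.075 mid-P.

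These results rest on a true rate ratio of 1, independent Poisson counts, the rates in Table 4 and an inferred comparator ratio. The statement in 9.9 that pediatric precision remains low can stand for the rarer endpoints. The table should be corrected, but the design does not depend on it.

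**What to change.** Recompute the six pediatric rows at 133,285 person-years by enumerating the two Poisson counts, with one named small-sample interval (exact or mid-P conditional). In the table note, state the interval, the comparator ratio and the assumed rate ratio of 1, and print the expected exposed cases beside each row.

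Revise the pediatric sentence in 9.5 to match. It currently gives 70% for lymphoma below 8, whereas Table 4 prints 0.46 below 8 and 0.70 below 16.

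The adult rows also reproduce at Phase I person-years, so their person-years need the same check. The normal formula may stay there, where expected exposed cases are at least 3.1 × 198,400/100,000 = 6.2 even at Phase I person-years.

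The cost is a few lines of code, a revised table and one revised sentence. Some low-threshold and CTCL figures become less favourable, and many others rise.

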9.2.3.2 Corticosteroids Cohorts

Topical corticosteroids have multiple indications of use. The two corticosteroids cohorts will be identified in each database from (1) all eligible individuals from the study population who have a diagnosis of atopic dermatitis at any time before the start date and received a prescription for moderate- to high-potency corticosteroids and (2) all eligible individuals without a diagnosis of atopic dermatitis any time before the start date who received a prescription for moderate- to high-potency corticosteroids during the study period and at least one other prescription within the prior 12 months (Figure 3). (See Section 9.3.1, Identification of Atopic Dermatitis, for further details on the atopic dermatitis criteria.)

Figure 3. Users of Moderate- to High-Potency Corticosteroids With Two Prescriptions Within a Period of 12 Months

Individuals meeting these criteria will be used to estimate propensity scores separately for the tacrolimus cohort and the pimecrolimus cohort. A person can be included in both corticosteroids cohorts, the comparative cohort for tacrolimus and the comparative cohort for pimecrolimus. The propensity score represents the predicted probability of receiving each corresponding treatment instead of receiving moderate- to high-potency topical corticosteroids. The percentiles of propensity scores estimated for each exposed cohort will be classified in 20 strata (twentiles). Users of corticosteroids will be frequency matched to users of tacrolimus and pimecrolimus according to the strata of propensity scores of each exposed cohort. A matching ratio (corticosteroids to tacrolimus or pimecrolimus) up to 4:1, depending on available matches, will be used across strata. The strata of propensity scores will be used to conduct an overall stratified analysis combining the data from the study databases. Separate propensity scores and strata of propensity scores will be calculated for the pediatric and adult populations.

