9.9 Limitations of the Research Methods

As in all safety studies, the relevant parameters to consider for the interpretation of the results focus on the point estimate, the upper limit of the confidence interval, and the absolute excess risk. A limitation of the study Phase I was the low precision of the estimated relative risks for most malignancies in the pediatric population and for lymphoma, particularly for CTCL, in adults. The JOELLE Extension study was planned to

improve the precision of the study through the inclusion of 4 additional years of data. Updated study size calculations show that the estimated precision of the effect estimates is improved, although it remains low in the pediatric population.

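### Table 4's probabilities, labelled JOELLE Extension, do not follow from Table 3's extension person-years at any comparator ratio from 1:1 to 4:1, and so understate the extension's precision

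*Protocol*

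**What the plan says.** Section 9.5 defines the precision measure as the probability of an "upper limit for the two-sided 95% CI of the rate ratio below the specific values of 2, 4, 8, and 16". The text puts it on the footing of the extension, "assuming a 4-year extension (additional 3-year period of inclusion plus 1 year of follow-up) and the incidence rates observed in Phase I", and the note under Table 4 repeats this: "Based on a 4-year extension (additional 3-year period of inclusion plus 1 year of follow-up) accounting for 6-month induction period".

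Table 3 gives, in order, Phase I users, Phase I person-years, extension users and extension person-years:

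- "Children aged < 18 years 19,948 50,316 24,412 133,285"
- "Adults aged ≥ 18 years 66,127 198,400 98,788 551,369"

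On comparators, section 9.2.3.2 says: "A matching ratio (corticosteroids to tacrolimus or pimecrolimus) up to 4:1, depending on available matches". Table 4 states neither the ratio nor the true rate ratio behind it.

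The text of 9.5 describes the pediatric probabilities as above those of Phase I but still low, and the adult ones as increased. It reports: "For Hodgkin lymphoma and CTCL, the probabilities are 95% and 85%, respectively, for having an upper limit below 4". Section 9.9 concludes: "Updated study size calculations show that the estimated precision of the effect estimates is improved, although it remains low in the pediatric population".

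**The concern.** Extension person-years are 133,285/50,316 = 2.65 times Phase I in children and 551,369/198,400 = 2.78 times in adults. With that much more exposure, about 2.8 pediatric lymphomas and 24 adult Hodgkin lymphomas are expected among tacrolimus users at a rate ratio of 1. The printed probabilities look too low for those counts.

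Table 4 is the protocol's only quantitative statement of the precision expected from the extension. Section 9.1 links the length of the extension to precision estimates, and 9.9 relies on them for its pediatric conclusion. Children are the population of particular concern in section 7.1. If the table rests on the wrong exposure, readers get a wrong picture of attainable precision exactly where it matters most.

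**Working it through.** **Inputs.** Incidence rates and stated probabilities: Table 4. Person-years: Table 3. Comparator ratio k: 1 to 4, since the maximum is 4:1. Assumptions, because the protocol does not state them: true rate ratio 1, and a normal approximation on the log scale.

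**Formula.** E = rate × tacrolimus person-years; SE = √(1/E + 1/(kE)); P(upper limit < X) = Φ(ln X/SE − 1.96).

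**Step 1: what reproduces the table.** Take Phase I person-years and k = 3.

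- Pediatric lymphoma: E = 2.1 × 50,316/100,000 = 1.057; SE = √(1.333/1.057) = 1.123; P = 0.090/0.234/0.457/0.694. Stated: 0.09/0.24/0.46/0.70.
- Adult Hodgkin lymphoma: E = 4.4 × 198,400/100,000 = 8.73; SE = 0.391; P = 0.426/0.944/1.00/1.00. Stated: 0.43/0.95/1.00/1.00.
- Adult CTCL: E = 6.15; SE = 0.466; P = 0.319/0.846/0.994/1.00. Stated: 0.33/0.85/0.99/1.00.

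All 48 cells agree, with a largest gap of 0.011. At k = 3.2, used for both age groups, the largest gap is 0.007. At k = 4 it is 0.025.

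**Step 2: the stated basis.** Take extension person-years.

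| k | Largest gap | Cells within 0.02 (of 48) |
|---|---|---|
| 1 | 0.245 | 23 |
| 2 | 0.37 | 22 |
| 3 | 0.41 | 20 |
| 4 | 0.43 | 20 |

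Most of the cells that match are adult cells at or near 1.00, which fit on almost any basis.

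**Step 3: other explanations.**

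- A different true rate ratio: over 0.3 to 3.9, at k = 1, 2, 3 or 4, the largest gap never falls below 0.19.
- Exact conditional limits: adult Hodgkin lymphoma below 2 becomes 0.60 (k = 1) or 0.90 (k = 4), against 0.43 stated.
- Fewer comparators than exposed: the table fixes only person-years × k/(1 + k). Extension person-years therefore fit at k ≈ 0.39, with a largest gap of 0.01.

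**Step 4: which table is at fault.** Sum interval midpoints × users in Tables 5 and 6, then subtract 0.5 year per user for induction.

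- Children: 146,020.5 − 0.5 × 25,479 = 133,281 (Table 3: 133,285).
- Adults: 602,953.5 − 0.5 × 103,175 = 551,366 (Table 3: 551,369).

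Table 3 agrees with the protocol's own follow-up distribution to within 4 person-years.

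**Step 5: values at extension person-years.**

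| Endpoint | Limit | Stated | 1:1 | 4:1 |
|---|---|---|---|---|
| Pediatric any lymphoma | 8 | 0.46 | 0.69 | 0.88 |
| Pediatric Hodgkin lymphoma | 8 | 0.37 | 0.57 | 0.78 |
| Adult Hodgkin lymphoma | 2 | 0.43 | 0.68 | 0.86 |
| Adult CTCL | 2 | 0.33 | 0.53 | 0.73 |
| Adult CTCL | 4 | 0.85 | 0.98 | 1.00 |

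The other adult rows are at or near 1.00 on either basis.

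**Step 6: text against table.** Section 9.5 gives pediatric lymphoma a 70% probability of an upper limit below 8. Table 4 shows 0.46 below 8 and 0.70 below 16.

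**The case against.** The best defence is that Table 4 does not disclose its comparator ratio, so the use of Phase I person-years is inferred. That stands. A reader might conclude that Phase I exposure is the only possible source, but a ratio of about 0.4 with extension person-years fits equally well. It would mean fewer than one comparator person-year for every two exposed. The protocol mentions no such assumption, and it is hard to square with matching up to 4:1.

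A reader might also infer that Table 3 overstates person-years by a factor of 2.65 to 2.78. Tables 5 and 6 do not support that. Their agreement shows internal consistency rather than independent confirmation, since all three tables probably come from one projection. The user totals in Tables 5 and 6 (25,479 and 103,175) also differ from Table 3's (24,412 and 98,788), although the person-years agree.

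That projection may be optimistic: only 1% of users have under one year of follow-up, which leaves little room for death or disenrollment. As a rough check for adults, assume even entry over 2012–2014 and no losses. Then 198,400 + 4 × 66,127 + 2 × 32,661 = 528,230 person-years, and adult Hodgkin lymphoma below 2 is 0.66 to 0.85. This is still far from 0.43.

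The error also runs in the conservative direction and changes no endpoint, cohort or analysis. That is correct and limits the consequences. Nor does Table 4 determine what an observed null result can exclude; the observed confidence limit will do that, and 9.9 interprets results on that basis. Finally, the statements that probabilities rose from Phase I cannot be shown false, because the protocol prints no Phase I probabilities. They are only unsupported by a table that Phase I person-years reproduce.

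**Conclusion.** The point holds. As labelled, Table 4 does not follow from Table 3 and its own incidence rates at any ratio from 1:1 to 4:1. The likely cause is that Phase I person-years were carried over, though this is not proven. The effect is to understate expected precision: by 0.23 to 0.42 for pediatric lymphoma below 8, 0.20 to 0.41 for pediatric Hodgkin lymphoma below 8, 0.25 to 0.43 for adult Hodgkin lymphoma below 2, and 0.20 to 0.40 for adult CTCL below 2.

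The recomputed values assume a true rate ratio of 1, the normal approximation and Table 3's person-years. They are what the protocol's own inputs imply, not a guarantee of realised precision. Pediatric precision against low limits stays modest even so: any lymphoma below 2 is only 0.13 to 0.18.

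**What to change.** Recompute Table 4 at Table 3's extension person-years. State under the table the comparator ratio, the assumed true rate ratio and the interval method. If a ratio well below 1:1 was really intended, say so and reconcile it with section 9.2.3.2.

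Then rewrite the precision statements in 9.5 and 9.9 from the new table. These include the adult Hodgkin lymphoma and CTCL sentence, the comparison with Phase I, and the pediatric lymphoma sentence that attaches 70% to the limit of 8.

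The cost is about an hour of recalculation and edits to one table and two paragraphs. No change to the design or to Table 3 is needed.

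### Section 9.5 states a 70% probability of an upper limit below 8 for pediatric lymphoma, but Table 4 gives 46% below 8 and 70% only below 16

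*Protocol*

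**What the plan says.** Section 9.5 explains that Table 4 gives, for each endpoint, the probability of an "upper limit for the two-sided 95% CI of the rate ratio below the specific values of 2, 4, 8, and 16". For children it first says that the probabilities have risen since Phase I but are still low. It then names lymphoma as a whole as the best-placed pediatric endpoint and credits it "with a 70% probability for having an upper limit of the 95% CI of the rate ratio below 8".

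The four probability columns of Table 4 stand under the heading "Probability That Upper Limit of the 95% CI of the Rate Ratio is Below", in the order 2, 4, 8, 16. The row for lymphoma under 18 years reads "Lymphoma 2.1 0.09 0.24 0.46 0.70", where 2.1 is the incidence per 100,000 person-years.

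Table 3 gives the tacrolimus person-years: 50,316 in Phase I and 133,285 in the extension for children, and 198,400 and 551,369 for adults. The title of Table 4 assigns it to the JOELLE Extension (2002-2015).

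**The concern.** The sentence pairs the probability from the last column (0.70, for 16) with the threshold of the column before it (8). A reader of the prose would think the study more likely than not to exclude an eightfold lymphoma rate in children. The table puts that chance slightly below one half.

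It matters because Section 7.1 describes children as the focus of the regulatory follow-up measure and as a particular concern, and this is the only pediatric precision figure given in the running text. Section 9.9 then relies on the updated study size calculations when it discusses pediatric precision.

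**Working it through.** **1. Direct lookup (no assumption needed).**

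| Upper limit below | 2 | 4 | 8 | 16 |
|---|---|---|---|---|
| Table 4, lymphoma, < 18 years | 0.09 | 0.24 | 0.46 | 0.70 |
| Section 9.5 text | – | – | 0.70 | – |

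Difference at 8: 0.70 − 0.46 = 0.24. No pediatric row exceeds 0.46 in the column for 8.

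**2. Are the table values in their proper columns?** With a true rate ratio of 1 and a normal approximation on the log scale, P(upper limit < L) = Φ(ln L / SE − 1.96). Solving each cell for SE gives 1.12, 1.11, 1.12 and 1.12. The row is coherent as printed. If 0.70 belonged to 8, SE would be 0.84 and the row would read about 0.13, 0.38, 0.70, 0.91.

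**3. The adult prose figures.** Non-Hodgkin lymphoma is 0.95 below 2, Hodgkin lymphoma 0.95 below 4 and CTCL 0.85 below 4 in the table, and the text agrees with each. Only the pediatric sentence departs from the table.

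**4. Which person-years does Table 4 reflect?** Take SE = √[(1/a)(1 + 1/k)], where a = incidence × tacrolimus person-years and k is the comparator ratio. The protocol allows up to 4:1 but does not say what Table 4 used, so k = 1 to 4 was tried.

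Pediatric lymphoma, Phase I person-years, k = 3:
- a = 0.000021 × 50,316 = 1.057
- SE = √(1.3333 / 1.057) = 1.123
- P(< 8) = Φ(2.079/1.123 − 1.96) = 0.457
- P(< 16) = Φ(2.773/1.123 − 1.96) = 0.694

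Extension person-years: a = 0.000021 × 133,285 = 2.799.

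| Pediatric lymphoma | < 2 | < 4 | < 8 | < 16 |
|---|---|---|---|---|
| Table 4 | 0.09 | 0.24 | 0.46 | 0.70 |
| Phase I, k = 3 | 0.090 | 0.234 | 0.457 | 0.694 |
| Phase I, k = 4 | 0.093 | 0.247 | 0.481 | 0.722 |
| Extension, k = 1 (SE 0.845) | 0.127 | 0.374 | 0.691 | 0.907 |
| Extension, k = 4 (SE 0.668) | 0.178 | 0.546 | 0.875 | 0.986 |

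Adults give the same picture. With 198,400 person-years and k = 3, Hodgkin lymphoma is 0.426 below 2 and 0.944 below 4 (table 0.43, 0.95), and CTCL is 0.319 and 0.846 (table 0.33, 0.85). With 551,369 person-years, even k = 1 gives 0.675 and 0.998 for Hodgkin lymphoma, and 0.526 and 0.982 for CTCL. Across all rows of Table 4, Phase I person-years at 3:1 reproduce every cell to about 0.01. Extension person-years miss some cells by more than 0.2 at every ratio tried.

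**5. Sensitivity to the approximation.** With an exact conditional interval and extension person-years, the pediatric lymphoma probability below 8 is 0.473 at 1:1 and 0.911 at 4:1.

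**The case against.** Three arguments can be made for leaving the sentence alone or treating it lightly.

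*The text may be right and the table wrong.* Extension person-years at 1:1 give 0.691 below 8, close to 70%. But the same inputs give 0.998 and 0.982 below 4 for adult Hodgkin lymphoma and CTCL, where the text says 95% and 85%. That variant does not explain the passage, and a column slip does. Even if it did, text and table would still disagree.

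*Nothing depends on the figure.* This largely stands. The ENCePP checklist in Annex 2 answers no to a hypothesis to be tested. No sample size, stopping rule or decision threshold uses the 70% or the bound of 8, the figure appears once, and the correct table entries follow in the same section. Section 9.5 and Section 9.9 both call pediatric precision low, and that reading is the same at 46% as at 70%. None of this makes the printed number right.

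*The extension may do better than 46%.* This also stands, and it limits the point. A reader might infer that the sentence overstates twofold, on the rate-ratio scale, what the extension can rule out. The documents do not support that, because it would require Table 4 to be a correct description of the extension. On the extension person-years the normal approximation gives about 0.69 to 0.88 below 8 for ratios of 1:1 to 4:1, so 70% could even be too low.

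**Conclusion.** The text contradicts the table exactly: 70% stated against 46% tabulated at a threshold of 8, with 70% belonging to 16. This finding needs no assumption.

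The further observation, that Table 4 appears to rest on Phase I rather than extension person-years, is an inference. It assumes a true rate ratio of 1, a normal approximation and a 3:1 ratio, none of which the protocol states for this table. For that reason the 24-point overstatement is measured against Table 4 only; it is not a measure of error against the extension's true precision, and 46% is not confirmed as the right extension figure.

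The protocol's view that pediatric precision is low stands if Table 4 is right. This is a correction to a stated precision figure, with no effect on the design or analysis.

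**What to change.** Confirm and state the person-years, comparator ratio and formula behind Table 4. If Phase I person-years were used, recompute the table with those of the extension and revise the figures in the prose of Section 9.5, adult as well as pediatric, to match. In either case make the pediatric sentence agree with the table's columns; if the table stands as printed, it should give 46% below 8 and 70% below 16.

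The cost is one sentence and a check of the study size calculation, plus a rerun of one table if the check shows it is needed. If the table stands, the stated pediatric figure becomes less favourable.
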